## Study Protocol:

### Objectives:

This research project aims to develop and test a Student Stress Management (SSM) mobile program, a suite of apps based within the framework of an evidence-based treatment for depression and anxiety that will be integrated within a student health system. This program will improve engagement with mental health services by serving as an access point to mental health treatment options, and providing an opportunity for self-guided treatment. The SSM program will feature components known to be effective both for engagement (symptom assessment and promotion of care accessibility) and treatment (thought restructuring, relaxation exercises, and behavioral activation). Within the suite, students will be prompted to complete symptom assessments on a weekly basis, and those with elevated symptom scores will be provided with feedback and recommendations for on-campus services. All users will be able to access and use interactive treatment apps. The program will be developed with the University of Illinois at Chicago (UIC) and Northern Illinois University (NIU) counseling centers, and will be made available to all UIC and NIU students. These studies will establish a research program that will expand the reach of services and ease the burden of untreated depression and anxiety for college students.

**Phase 1 Aim: Develop the SSM program by refining a mobile smartphone intervention and develop an optimized multi-component implementation strategy using a user-centered design process.** We will start from a suite of apps developed for a general population and, based on needs reported by current students and mental health care providers, they will be optimized for the college student population alongside development of an implementation plan and evaluation metrics. Laboratory-based usability testing and an 8-week field trial will be included as part of the iterative design process to ensure that SSM works optimally both in individual interactions, as well as cumulatively over time.

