**Phase 2 Aim: Conduct a trial of the SSM program within two university communities.** The overall aim of this study is to pilot the SSM program, evaluation metrics, implementation strategies, data collection and assessment procedures for a larger implementation trial. Counseling center utilization will be measured for one academic year to obtain a baseline for both sites. One site will be randomly selected and the SSM program will be implemented, while the other site will continue to collect baseline data. After one academic semester, the additional implementation strategies will be incorporated for an enhanced implementation plan, and both study sites will receive the enhanced implementation plan for one semester. During the implementation phases, counseling center utilization and SSM program use, will be tracked.

**Hypothesis 1:** Introduction of the SSM program will impact utilization of counseling center resources, and the use of an enhanced implementation plan will increase program penetration (e.g., app downloads) and strengthen its impact on utilization. We will explore multiple metrics to assess program impact on utilization, and hypothesize the number of appointments for crisis and follow-up will 1) be reduced during implementation relative to pre-implementation and 2) will be reduced in enhanced implementation relative to initial implementation. We will also explore the impact of implementation on seasonal variations in

counseling center utilization, level of depressive symptoms (as measured by the PHQ-9) at intake, and any other evaluation metrics identified during Phase 1.

**Hypothesis 2:** Sustained use of the SSM program will result in reductions in depression and anxiety among individual users, and these reductions will be mediated by increases in mental health literacy, knowledge of mental health care services, and cognitive and behavioral coping skills.

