### **Procedures Involved:**

Monthly data on engagement with counseling center services will be collected from the counseling center’s Titanium Electronic Medical Record (EMR) to serve as a predeployment “baseline” for Phase 2. For the primary outcome of counseling center resource utilization, we will compare the predeployment phase (the 2 semesters prior to program implementation) to the implementation phases. During the predeployment phase, weekly data will be collected from existing service records at the counseling centers at UIC and NIU on new counseling appointments, follow-up appointment, group therapy appointments and crisis appointments. The data will be reported in aggregate and will not include individual personal identifiers. The SSM program will first be implemented in one study site (UIC or NIU – chosen via random selection) using the initial implementation plan (e.g. advertisements, identification of early adopters, identification of student leaders to serve as champions) designed in Phase 1. Data from individual interviews will be gathered from the first study site will inform an enhanced implementation plan. During this third semester, predeployment data will also be collected at Site #2. Then, the enhanced implementation plan, updated based on the semester 3 deployment at Site #1, will be deployed at both study sites and data will be collected for an additional semester. When the implementation begins on each campus, the program will be made freely available to download, and counseling center intake paperwork will be modified to ask students if they used the SSM program which allows for tracking of counseling center referrals while maintaining patient confidentiality. This design allows us to examine: a predeployment phase for both sites, an initial phase of implementation for Site #1, and an enhanced implementation phase for Site #1 and for Site #2. A strength of this implementation design is that it allows for learning within itself by comparing initial implementation strategies with an enhanced implementation plan. This process of learning and adapting is key for effective and sustainable implementation. Staggering the start times of implementation allows for within-site targeted comparisons of effect of introducing the SSM program on utilization of the counseling center in each site, and for an exploration of between-site differences in the impact of the enhanced implementation plan.

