The study utilizes an interrupted time-series design, which offers a number of benefits over large-N designs and has been shown to be an acceptable approach for examining treatment efficacy as well as a useful design for rigorous implementation research when few sites are

involved. There are both scientific and pragmatic benefits to introducing a program into a system with this design approach. Since these time-series measurements are recorded on a weekly basis, one can observe how change unfolds across time, examine seasonal effects to better evaluate change in these centers that are often at capacity, and investigate the trajectory of change. Because all members of the campus community are granted access to the program, this design meets the needs of community stakeholders.

To examine outcomes for Hypothesis 2 (sustained use of the SSM program will result in reductions in depression and anxiety among individual users, and will be mediated by increases in mental health literacy, knowledge of mental health care services, and cognitive and behavioral coping skills), we will examine longitudinal data from individual users regarding depression and anxiety symptoms, mental health literacy, knowledge and beliefs about mental health care services, barriers to mental health care, and cognitive and behavioral coping skills to determine if sustained program use is associated with changes in these measures.

*SSM Program:* The program will prompt users to complete repeated symptom assessments and provide psychoeducation regarding current symptoms while encouraging students in need to utilize available campus services. Upon download, the Student Hub app will prompt users to complete the PHQ-8 and GAD-7 and will provide feedback on symptoms. Based on symptom scores, users will receive automated feedback about depression/anxiety, availability of mental health and wellness services on campus, and information and interactive digital tools to support continued stress management and wellness. Users will be prompted with ability to use interactive self-help tools within the app suite. Interactive, clinical apps (designed for daily use) are included to facilitate engagement with mood monitoring, and to appeal to a preference for self-reliance.

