**Statistical Analysis Plan:**

We used a mixed-methods approach to analyzing the impact of the IntelliCare for College Students program, in that we analyzed quantitative data on app usage and counseling center utilization alongside qualitative data generated through interviews with students and staff.

Demographic data were examined primarily in the form of descriptive statistics, and chi-square tests and a student's t-test were used to examine potential demographic differences between the participants who consented to the study that did (n=117) and did not (n=65) download and register their participant ID to the IntelliCare for College Students app. App usage data were examined in the form of descriptive statistics.

Due to missing data throughout the trial, multiple imputation methods and separate generalized linear mixed models to account for repeated measures from each participant over time, were used to examine symptoms of depression and anxiety at baseline, week 1, week 2, week 4, week 6 and week 8, and anxiety literacy, depression literacy, and cognitive and behavioral coping skills at baseline, month 1 and month 2.

To examine symptom assessments longitudinally, we fit the available weekly symptom assessment data into a structure of baseline, week 1, week 2, week 4, week 6 and week 8 timepoints. Only 2 individuals had complete data. A total of 48 participants only completed the symptom assessment at one time period, 16 (17) completed 2 of the 6 assessments (16 for GAD, 17 for PHQ), 3 (2) completed 3 of the 6 assessments, 5 had 4 of the 6 assessments, and 5 were missing just one assessment. Multiple imputation methods were used to account for missing data. Participants were also prompted to complete measures of our mental health intervention targets on a monthly basis within the app. Many participants did not complete these assessments, and data were examined at baseline, month 1, and month 2. Multiple imputation methods were used to account for missing data.

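### Symptom scores are fitted into six slots ending at week 8, and monthly measures into three ending at month 2, with no reason given, although prompting has no stated end and most slots are empty

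*Combined protocol and SAP*

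**What the plan says.** All references are to the combined protocol and SAP.

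- **Symptom grid.** The Statistical Analysis Plan section fits the available weekly depression and anxiety scores "into a structure of baseline, week 1, week 2, week 4, week 6 and week 8 timepoints". It gives no windows for assigning a score to a slot and no reason for ending at week 8.
- **Monthly grid.** For literacy and coping, participants were "prompted to complete measures of our mental health intervention targets on a monthly basis within the app". The SAP then states: "Many participants did not complete these assessments, and data were examined at baseline, month 1, and month 2".
- **Prompting.** Under Objectives, "students will be prompted to complete symptom assessments on a weekly basis". No end date is given for either kind of prompt.
- **Deployment.** At the first site, the Phase 2 Aim says: "After one academic semester, the additional implementation strategies will be incorporated for an enhanced implementation plan". Procedures Involved adds that the enhanced plan "will be deployed at both study sites and data will be collected for an additional semester". That makes two semesters at Site 1 and one at Site 2. The SAP says the enhanced strategy could not be enacted in the second semester of implementation, so a second semester did take place.
- **Hypothesis.** Hypothesis 2 reads: "Sustained use of the SSM program will result in reductions in depression and anxiety among individual users". Procedures Involved says longitudinal user data will be examined "to determine if sustained program use is associated with changes in these measures". Neither place defines sustained use or sets a follow-up length per student. The only 8-week period in the protocol is the Phase 1 field trial.

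**The concern.** Two features of the grid cost information or clarity.

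First, a weekly series is reduced to six points. A student who answered at weeks 3 and 5 but not at week 4 has a missing week-4 slot, unless an unstated window moves one of those scores into it. The SAP then fills gaps by multiple imputation. A real score may therefore be left out or shifted in time while a value nearby is imputed.

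Second, the end point is unexplained. It appears only in the SAP, which is written in the past tense and reports completion counts, so it was set down with the data in hand. A horizon that is shorter than the deployment and is first stated at that stage needs a reason, particularly for a hypothesis about sustained use. At stake is how precisely and clearly the plan can describe change over time, and how far a Hypothesis 2 conclusion may reach beyond the first 8 weeks.

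**Working it through.** The plan gives no sample size, power or target precision for Hypothesis 2, so there is no stated figure to reproduce. Three checks were made.

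**1. How full the grid is.** Inputs are the completion counts in the Statistical Analysis Plan section, as people by number of slots filled:

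| Slots filled | Anxiety (GAD) | Depression (PHQ) |
|---|---|---|
| 1 | 48 | 48 |
| 2 | 16 | 17 |
| 3 | 3 | 2 |
| 4 | 5 | 5 |
| 5 | 5 | 5 |
| 6 | 2 | 2 |
| People | 79 | 79 |

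- Slots available: 79 × 6 = 474.
- Filled, GAD: 48 + 32 + 9 + 20 + 25 + 12 = 146, and 146/474 = 30.8%, so 69.2% are empty.
- Filled, PHQ: 48 + 34 + 6 + 20 + 25 + 12 = 145, and 145/474 = 30.6%, so 69.4% are empty.
- One slot only: 48/79 = 60.8%. Two or more: 31. Five or six: 5 + 2 = 7.
- The SAP reports 117 registered users; 117 − 79 = 38 are in no completion category. It does not say whether 79 or 117 were imputed.

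**2. What the grid leaves without a slot up to week 8.** Weekly prompting gives baseline plus 8 weeks, or 9 possible scores. The grid has 6 slots, so weeks 3, 5 and 7 (3 of 9) have none of their own.

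**3. Upper limit on what could lie after week 8.** Semester length is not in the documents. Assume 15 weeks (range 14 to 18), registration at launch, a prompt every week until deployment ends, no break between semesters and every prompt answered. Possible scores = weeks + 1; later scores = weeks − 8.

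| Deployment | Possible scores | After week 8 | Share |
|---|---|---|---|
| One semester, 15 weeks | 16 | 7 | 44% |
| One semester, 14 to 18 weeks | 15 to 19 | 6 to 10 | 40% to 53% |
| Two semesters, 30 weeks | 31 | 22 | 71% |
| Two semesters, 28 to 36 weeks | 29 to 37 | 20 to 28 | 69% to 76% |

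These are ceilings on opportunity, not estimates of recorded data. The counts in check 1 cover only the six slots, so they show neither that later scores exist nor that they are absent.

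**The case against.** The strongest reply is that stopping where data become thin is a defensible choice. Only 31 of 79 people fill two or more slots and only 7 fill five or six. A curve carried to about week 30 would rest on a few persistent, self-selected responders. This stands, and it is why week 8 should remain the main estimate. It does not excuse the missing reason.

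A reader might also infer more than the documents support:

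- *That late scores were collected and thrown away.* Nothing says that any score was recorded after week 8 or that one was excluded. Without windows, a week-9 score may even sit in the week-8 slot.
- *That every student was prompted for one or two semesters.* Those are site-level periods. Students could download at any time after launch, so a late registrant may have little or no time beyond week 8.
- *That 44% or 71% of the data is lost.* These figures hold only at the ceiling described above.
- *That later scores are the most relevant ones for sustained use.* The term is undefined, and a late questionnaire does not measure how much the apps were used. The SAP treats app usage only descriptively, so a longer time axis would still leave use out of the model.
- *That week 8 was picked to suit the results.* The text shows only that the end point is unexplained and was written down after completion was known.

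The coarse grid, the missing windows and the unexplained end point survive these objections.

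**Conclusion.** The concern holds in a limited form. The SAP puts weekly scores into six slots and monthly measures into three, with no windows and no reason for ending at week 8 and month 2. Weeks 3, 5 and 7 and anything later have no slot of their own, while about 69% of the six slots are empty among the 79 people counted.

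The 69% rests on reading the SAP's counts as slots filled out of six. How many scores lie off the grid, before or after week 8, is not stated, so the gain from using them cannot be calculated; after week 8 it may be small. As written, the plan supports a statement about change over 8 weeks (2 months for the monthly measures) and nothing longer.

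**What to change.** 1. Keep every recorded score with its date. Fit the mixed models with time as continuous weeks since registration, linear or a low-order spline. Keep estimated change at week 8 as the main estimate for symptoms, and at month 2 for the monthly measures.
2. A likelihood-based mixed model accepts unequally spaced scores directly. If multiple imputation is retained, its model should also use the off-slot scores.
3. As a supplementary analysis, include scores after week 8 and report change at a fixed later week since registration, only as far as the data support it and with the number of people observed. A calendar point such as the end of the semester falls at a different week for each registrant and should not be used on this axis.
4. State how long students were prompted, how scores were assigned to slots, how many scores and people fall after week 8 and month 2, and why the grids end there. If almost no later scores exist, say so and limit the Hypothesis 2 conclusion to change over 8 weeks.

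The cost is SAP wording and a re-run on data already recorded; no new data collection is needed. The downside is that late estimates would rest on few, self-selected responders and must be labelled as such.

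### Most follow-up PHQ and GAD slots are empty (about 83% on the likeliest reading), and the plan fills them by multiple imputation with no sensitivity analysis described

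*Combined protocol and SAP*

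**What the plan says.** The Objectives section says that "students will be prompted to complete symptom assessments on a weekly basis". Procedures Involved adds the starting point: "Upon download, the Student Hub app will prompt users to complete the PHQ-8 and GAD-7". Hypothesis 2 reads: "Sustained use of the SSM program will result in reductions in depression and anxiety among individual users".

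The Statistical Analysis Plan is written in the past tense and describes how the weekly scores were arranged: "we fit the available weekly symptom assessment data into a structure of baseline, week 1, week 2, week 4", followed by weeks 6 and 8. It then gives the completion counts, beginning "Only 2 individuals had complete data. A total of 48 participants only completed the symptom assessment at one time period", and states twice: "Multiple imputation methods were used to account for missing data". The imputation is paired with separate generalized linear mixed models for repeated measures.

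On logged use it says: "App usage data were examined in the form of descriptive statistics". On the monthly literacy and coping measures it says: "Many participants did not complete these assessments, and data were examined at baseline, month 1, and month 2". These were also imputed, but no completion counts are given.

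Neither the protocol nor the SAP states the imputation model, the set of people imputed, any auxiliary variables, the assumption about the missing values, the observed n per time point, or a sensitivity analysis. The only group comparison is demographic, between the 117 who registered in the app and the 65 who did not.

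**The concern.** When most follow-up values are imputed, the estimated symptom change depends mainly on what the imputation assumes about people who stopped reporting. Standard multiple imputation assumes that, given the observed data, those who stopped would have followed the same course as those who continued. A likelihood-based mixed model on the observed scores makes the same kind of assumption, so pairing the two methods is not a check on either.

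The assumption is hard to take on trust here. The scores are prompted inside the program, so someone who stops opening it plausibly also stops being measured. Hypothesis 2 is about sustained use, so missingness is plausibly tied to the exposure of interest. Properly pooled imputation widens the intervals to reflect the amount of missing data, but it does not protect against a wrong assumption about it.

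At stake is any statement that symptoms improved among users. Without a sensitivity analysis, a reader cannot tell how far such a statement rests on observed scores and how far on the assumption.

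**Working it through.** **Inputs.** Six time points (baseline and five follow-ups) and the completion counts, all from the Statistical Analysis Plan. The plan states no total and no missing percentage, so there is no figure of its own to reproduce.

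| Slots filled | GAD, people | PHQ, people |
|---|---|---|
| 1 | 48 | 48 |
| 2 | 16 | 17 |
| 3 | 3 | 2 |
| 4 | 5 | 5 |
| 5 | 5 | 5 |
| 6 | 2 | 2 |

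**Step 1, people.** GAD: 48+16+3+5+5+2 = 79. PHQ: 48+17+2+5+5+2 = 79.

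**Step 2, filled slots** (sum of slots × people). GAD: 48+32+9+20+25+12 = 146. PHQ: 48+34+6+20+25+12 = 145. Each is out of 79×6 = 474.

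**Step 3, results that need no timing assumption.** One slot only: 48/79 = 60.8%. Two or more: 79−48 = 31 people. Four or more: 5+5+2 = 12 people. Successive within-person differences number (slots−1) per person. GAD: 16+6+15+20+10 = 67. PHQ: 17+4+15+20+10 = 66. The 12 people with four or more slots supply 15+20+10 = 45 of these, or 67% (GAD) and 68% (PHQ).

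**Step 4, follow-up slots if the first score is baseline and the 79 are imputed.** Filled: 146−79 = 67 (GAD) and 145−79 = 66 (PHQ), out of 79×5 = 395. Empty: 1−67/395 = 83.0% and 1−66/395 = 83.3%. On average, 67/5 = 13.4 and 66/5 = 13.2 scores are observed per follow-up time point.

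**Step 5, other readings.** The consented total is 117+65 = 182.

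| Imputed set and timing | GAD filled / slots | Empty, GAD (PHQ) |
|---|---|---|
| 31 people with two or more slots, first score = baseline | 67/155 | 56.8% (57.4%) |
| 79 people, only the 2 complete cases have baseline | 144/395 | 63.5% (63.8%) |
| 79 people, first score = baseline | 67/395 | 83.0% (83.3%) |
| 117 registered, first score = baseline | 67/585 | 88.5% (88.7%) |
| 182 consented, first score = baseline | 67/910 | 92.6% (92.7%) |

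More than half of the follow-up slots are empty in every row. Getting below half takes the smallest set and the extreme timing together: GAD (146−48−2)/155 = 96/155 filled, 38% empty. That timing sits poorly with a prompt at download.

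**Step 6, leverage of the assumption.** Adding a shift of delta points to every empty follow-up slot moves the average follow-up mean by delta × (share empty). On the step 4 reading this is 0.83 points per 1-point delta. A delta of 1/0.83 = 1.20 times the imputed mean change therefore brings that change to zero. At 56.8% empty the multiple is 1/0.568 = 1.76, and at 92.6% it is 1/0.926 = 1.08.

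**The case against.** The strongest reply has four parts.

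*The 83% is not the plan's figure.* It needs two unstated assumptions, and the counts are of filled slots, not raw scores. Weeks 3, 5 and 7 have no slot, and the text does not say whether those scores were merged or dropped, so part of the gap may come from the slot structure. This stands, and it is why 83% is given as one reading with others beside it. The 61% with a single slot needs neither assumption.

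*Missingness may be harmless, or already modelled.* A reader might infer that the scores are missing not at random, that improvement is overstated, or that app use was left out of the imputation. The documents support none of these. They do not show that non-reporting equals non-use, they report no symptom result, and a descriptive summary of app use does not exclude its use as an auxiliary variable. An undocumented sensitivity analysis may also exist. What remains is that none is described and that the direction of any bias is unknown.

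*A tipping point always exists.* Asking a result to survive a delta series means nothing unless the range of deltas is bounded. Imputation centred on no change is itself only one assumption, and it builds in attenuation for the 48. Both objections stand and shape the fix.

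*The weight is limited.* Phase 2 is a pilot for a larger trial, the SAP discloses the sparse completion openly, and no control group is described for symptom scores, so even complete data would not attribute change to the program. This limits the importance of the point without removing it.

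**Conclusion.** The point holds as a low-cost improvement. Per scale, 79 people have at least one filled slot and 48 of them (61%) inform no within-person change. About 83% of follow-up slots are empty if the first score is baseline and the 79 are the imputed set. The prompt at download makes the first assumption likely. The second is implied by the counts but not stated. Varying the imputed set gives about 57% to 93%.

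A statement about symptom change under Hypothesis 2 would therefore rest largely on an assumption that is doubtful in this setting and that no described analysis examines. This does not show that any estimate is wrong or in which direction it might err. A reader might also extend the point to the trial's main result, but the primary outcome is counseling center utilization from aggregate service records, which does not depend on these scores.

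**What to change.** 1. **Sensitivity analysis.** Add a delta-adjusted version of the imputed mixed model, shifting the values in the empty follow-up slots. State the range of deltas and its rationale before running it. Report the tipping point, and qualify any statement of symptom improvement by whether it holds across that range. An imputation centred on no change may be shown as one reference scenario, not as a pass/fail test.
2. **Use of logged app data.** If not already done, include one simple summary of app use as an auxiliary variable in the imputation. Drop it, with a note, if the model does not converge. Compare baseline scores and app use descriptively for the 48 people with one filled slot and the 31 with two or more.
3. **Reporting.** State who was imputed, the observed n per time point, and how weekly scores were assigned to the six slots, including whether any were dropped.
4. **Monthly measures.** Apply items 1 to 3 to the literacy and coping measures and give their completion counts.

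The cost is SAP wording and a modest re-analysis of data in hand. The downside is probably a less certain statement of improvement. The sensitivity analysis does not supply a control group, so it cannot by itself support attributing change to the program.

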
member contact information, and a link prompting students to complete an online consent and eligibility screening measure via REDCap. For those who do not respond to the recruitment email, a “nudge” email will be sent to remind participants 7 days after first contact. The consent form describes the study, discusses participant roles and responsibilities and risks, informs participants that their data will be confidential and de-identified data will be used for research purposes only, and provides important contact information. Participants will agree to participate by checking a “yes” box and typing in their name. Once consent is received, another email will be sent to schedule interviews with students and share Zoom meeting information. Reminder emails will be sent 24-48 hours in advance and day of. These recruitment procedures are similar to those that have been approved by the Northwestern University IRB for prior studies conducted by our lab group.

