**Confidentiality:**

Data for all participants will be kept strictly confidential, except as mandated by law. All research files are kept on secure, password protected Northwestern University departmental and medical school servers. All electronic data will be stored on secure servers behind firewalls meeting all security requirements of the medical school. Any paper documentation is kept in locked file cabinets or a locked file room. Participants will be assigned a numerical code for identification in the files. Names and other identifiers will be kept in separate password protected files. Audio data will be stored on secure servers and will only be available for coding by study staff. Online assessments will be conducted on REDCap. This platform uses up to date security measures that are consistent with those used by Electronic Medical Records and are HIPAA compliant. All data collected via the interventions (e.g. mobile application) and assessments are transmitted using Transport Layer Security (TLS) encryption to prevent eavesdropping and tampering information while it is in the transmission pipeline. In addition, all data stored within the intervention is de-identified with a unique key. We will instruct patients on how to add a PIN to their phone to prevent unwanted access. We will clearly inform the patients of the risk of data insecurity. All data presentation will be of aggregate-level data; participants are never individually named.

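### Every described route for collecting Hypothesis 2 outcomes is an in-app prompt, so missing outcomes are probably tied to disengagement, and the imputation has no stated missingness assumption or sensitivity analysis

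*Combined protocol and SAP*

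**What the plan says.** The second hypothesis, in the Objectives section, is that "Sustained use of the SSM program will result in reductions in depression and anxiety among individual users", with literacy, knowledge of services and coping skills as mediators. The exposure is therefore continued use of the app.

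Three places describe how the outcomes are obtained:

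- Objectives, on symptoms: "Within the suite, students will be prompted to complete symptom assessments on a weekly basis".
- Procedures Involved, on the first symptom score: "Upon download, the Student Hub app will prompt users to complete the PHQ-8 and GAD-7 and will provide feedback on symptoms".
- Statistical Analysis Plan, on the mediators: "Participants were also prompted to complete measures of our mental health intervention targets on a monthly basis within the app".

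The Confidentiality section adds, without saying which assessments it means: "Online assessments will be conducted on REDCap". The one specific Phase 2 use of REDCap, under Study-Wide Recruitment Methods, belongs to the interviews with students who had not used the program: "a link prompting students to complete an online consent and eligibility screening measure via REDCap".

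The Statistical Analysis Plan handles missing outcomes by multiple imputation with generalized linear mixed models. It gives no imputation model, missingness assumption or sensitivity analysis. App usage is summarised descriptively and is not related to assessment completion.

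**The concern.** Exposure and outcome observation share one channel. If a student who loses interest in the app also stops answering its prompts, the low-use students whom Hypothesis 2 needs for comparison are the ones with few or no follow-up scores. Symptom change then rests largely on students who chose to continue. If continuing is related to how a student is faring, beyond what the recorded data explain, the estimated change is biased. An imputation that assumes missing at random would carry the completers' trajectory over to those who left, and the observed data cannot test that step.

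This matters beyond the present analysis. The Phase 2 aim includes piloting "data collection and assessment procedures for a larger implementation trial", so the yield of the assessment procedure is one of the things this phase was meant to find out.

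**Working it through.** The documents give no sample size, power or effect size for Hypothesis 2, so there is no design figure to reproduce. The check is a tally of the reported completion counts, followed by an illustration of possible bias.

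**Inputs (Statistical Analysis Plan).** 182 consented = 117 who registered in the app + 65 who did not. Symptom assessments completed, out of six timepoints:

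| Completed | GAD | PHQ |
|---|---|---|
| 1 | 48 | 48 |
| 2 | 16 | 17 |
| 3 | 3 | 2 |
| 4 | 5 | 5 |
| 5 | 5 | 5 |
| 6 | 2 | 2 |

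**Step 1: students with any score.** GAD 48+16+3+5+5+2 = 79; PHQ 48+17+2+5+5+2 = 79. The two tallies agree.

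**Step 2: scores observed** (sum of timepoints × students).
- GAD: 48+32+9+20+25+12 = 146.
- PHQ: 48+34+6+20+25+12 = 145.
- Possible for 79 students: 79 × 6 = 474, so 146/474 = 30.8% and 145/474 = 30.6%.
- Possible for 117 registrants: 117 × 6 = 702, so 146/702 = 20.8% and 145/702 = 20.7%. This assumes that the 79 are a subset of the 117, which the documents do not state.

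**Step 3: students who can show within-person change.** 79 − 48 = 31. That is 31/79 = 39% of those with any score and 31/117 = 26% of registrants (same assumption). Four or more scores: 5+5+2 = 12, or 12/79 = 15%. Completeness of the monthly mediator measures is not quantified.

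**Step 4: illustration of selection bias.** All inputs here are assumptions: true mean change zero; improvement normally distributed with SD 4 to 5 points; having a repeat score follows a logistic model with odds ratio 1.35 to 1.5 per SD of improvement, with the intercept set so that the average retained share is 31/79 or 31/117. With p(z) the retention probability at standardised improvement z, the false mean change in those retained is

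SD × E[z·p(z)] / E[p(z)].

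By numerical integration:

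| Retained | OR | Bias in SD units | SD 4 | SD 5 |
|---|---|---|---|---|
| 31/79 | 1.35 | 0.179 | 0.71 | 0.89 |
| 31/79 | 1.5 | 0.237 | 0.95 | 1.19 |
| 31/117 | 1.35 | 0.217 | 0.87 | 1.08 |
| 31/117 | 1.5 | 0.289 | 1.16 | 1.44 |

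**Step 5: comparison with sampling error.** SD/√31 gives 4/5.57 = 0.72 and 5/5.57 = 0.90. At the same SD, the bias is about 1.0 to 1.3 standard errors with 79 as denominator and 1.2 to 1.6 with 117. If students who improve are the ones who leave, the sign reverses.

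**The case against.** Much of the case on the other side stands, and it rules out several stronger readings.

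- *A reader might infer that outcomes were recorded only when the app was opened, and go missing exactly when use stops.* The documents do not show this. They are silent on off-app follow-up, and the Confidentiality sentence leaves room for it. A student can keep using the clinical apps and ignore the prompts, and nothing cross-tabulates use with completion. A link between the two is likely; identity is not shown.
- *A reader might see a contradiction between REDCap and in-app collection.* The Confidentiality section covers the whole project and mentions data from the interventions and from assessments as two streams. It is unspecific, not contradictory, and does not show that REDCap follow-up of app users was available.
- *A reader might count all 182 consenters and quote 31/182 = 17%.* The 65 who did not register left before any exposure to the app, so improvement on it cannot explain their absence, and the hypothesis concerns users. That denominator overstates the bias.
- *A reader might conclude that multiple imputation cannot work here.* It is valid if missingness depends only on recorded data included in the model. The fair criticism is that this assumption is neither stated nor tested.
- The Step 4 figures describe a complete-case mean change. They do not estimate the bias of the imputed mixed-model analysis.
- In-app assessment is partly deliberate: repeated symptom scoring with feedback is a component of the program, in a pilot focused on uptake with no set sample size.

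None of this supplies a described off-app route, a missingness assumption or a sensitivity analysis.

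**Conclusion.** The point holds as a likely dependence that has not been examined. It does not establish a bias of known size. The described collection of symptoms and mediators runs through the intervention whose use is the exposure. About 69% of the six-timepoint grid is empty even among the 79 students with any score, and that heavy loss is compatible with disengagement as well as with skipped prompts. On the assumed inputs, modest selection yields a false change about as large as the standard error or larger, in either direction. A symptom reduction reported from these data could therefore reflect who kept answering. The mediation part of the hypothesis has the same weakness, with completeness unreported.

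The Statistical Analysis Plan is written in the past tense. A reader might infer that a protocol amendment could still recover follow-up scores for this trial; it could not. What can still change here is the analysis, the reporting and the strength of the conclusion.

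**What to change.** **For this trial (analysis and reporting only):**

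1. Report assessment completion by level of app use, for symptoms and for the monthly measures, and say how the 79 relate to the 117 registrants.
2. State the imputation model and its missingness assumption. Add a missing-not-at-random analysis in which imputed scores are shifted by a range of deltas in both directions, and report the delta at which the conclusion changes.
3. Limit the Hypothesis 2 conclusion to students who kept completing in-app assessments.
4. State which assessments the Confidentiality section places on REDCap.

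These steps need analyst time and no new data.

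**For the assessment procedure carried to the larger trial:** send the same PHQ-8, GAD-7, literacy and coping measures by automated REDCap link at consent, week 4 and week 8 to every consenter, whether or not the app is registered or opened. Make these the outcome source for Hypothesis 2 and keep in-app scores as supportive data. REDCap is already named in the protocol and consent is digital, so the added set-up should be modest. The price is more survey burden, extra contact in a naturalistic rollout, and survey non-response. The documents give no response rate. Purely as an assumed range, 50% to 80% of 117 would be about 58 to 94 students at a follow-up timepoint, against at most 31 with any second score now. Non-response would remain, but it would no longer be built into app use.
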